3.2 Final statistical analysis plan

The primary outcome for efficacy is the rate of symptomatic CSDH ipsilateral recurrences requiring reoperation within 6 months. The statistical analysis for efficacy will be performed according to both the ITT and PP principles. The ITT analysis will be performed using the full analysis set, defined as all randomized patients in the groups allocated by randomization. No exclusions other than those caused by missing information will be made. No imputation will take place. The PP analysis will be performed on the subset of the full analysis set that is compliant with the protocol, has completed treatment, has available measurements, and has no major protocol violations or entry criteria violations.

As the goal of CSDH surgery is not only to prevent reoperations but also to improve neurological function and prevent death, the entire therapeutic effect (value) of intraoperative irrigation (versus no irrigation) may not be sufficiently comprehensively captured by analysing the primary outcome (rate of reoperations) only. For example, any possible between-group differences in the incidences of deaths and unfavorable functional outcomes may have an effect on the likelihood of a patient being considered for reoperation (i.e., skew the primary analysis).

Prompted by this realization, we deemed it necessary to somehow take into account between-group differences in either mortality and/or unfavorable functional outcome (mRS 0–3 vs. 4–6) in interpreting the findings of the FINISH trial. The approach, to be used in the blinded data interpretation (BDI) [8] of the FINISH trial, is outlined below. In addition, in the event that we will observe a statistically significant difference in the number of deaths

between the two groups, we will carry out a detailed analysis of the causes of death by examining the official death certificates of the participants.

We will claim treatment non-inferiority only if:

- 1) Our primary efficacy analysis, based on the primary outcome, shows non-inferiority and the finding is supported both by the ITT and the PP analyses,
and
- 2) there are no relevant between-group differences in mortality (alive or dead at 6 months) or unfavorable functional outcome (mRS 0–3 vs. 4–6 at 6 months) between the groups (according to an approach outlined in the BDI).

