Summary statistics will be presented for both groups. Continuous variables will be presented in terms of mean values or medians with SDs and IQRs, respectively. Categorical variables will be presented with relative frequencies in percent.

The results from the statistical analysis will be considered to support a claim of non-inferiority if the upper limit of a one-sided 97.5% CI (or equivalently a 95% two-sided CI) excludes a difference in the primary endpoint in favor of the irrigation group of more than 7.5%. The center stratification of the randomization will be accounted for in the calculation of the CI.

Exploratory analyses of secondary and other binary endpoints will be performed using the χ^2 test or logistic regression analysis. Continuous outcomes will be analyzed using regression Student's t-test, analysis of covariance or regression models.

Potential effect modifiers will be analyzed by including interaction terms in statistical models for the following subgroups:

- patient age (<70 years, \geq 70 years)
- GCS score at baseline (9–12, 13–14, 15)
- history of head trauma (<4 weeks, \geq 4 weeks, head trauma with unknown timing, no head trauma)
- unilateral versus bilateral CSDH
- use of anticoagulation and/or antiplatelet medication versus none
- preoperative mRS (0–3, 4–5)
- hematoma density (isodense, mixed-density, hypodense)
- hematoma size (width in mm)
- presence of membranes on preoperative imaging (yes, no)

The primary endpoint will be investigated as described above using a CI, which is equivalent to using a non-inferiority test with a one-sided p-value of 0.025 (or a two-sided of 0.05). The between-group comparison of 6-month mortality and mRS 4–6 differences will be compared using 85% and 95% CIs (as outlined in more detail in the BDI). The statistical testing of other endpoints will also be performed using a two-sided significance level of 0.05.

STATA (Statistics/Data analysis, SE v15.1, StataCorp LLC, [name]) will be used for analyses.

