Given that the objective of surgery for CSDH extends beyond preventing reoperations to also encompass the improvement of neurological function and prevention of death, the entire treatment effect of intraoperative irrigation (versus no irrigation) may not be adequately captured by focusing solely on the primary outcome measure, the rate of reoperations. We deemed it crucial to also consider the potential impact of between-group differences in deaths and/or unfavorable functional outcomes, as both could have an effect on the rate of reoperations. We felt that in the name of transparency and trustworthiness, we would need to define *a priori* thresholds for between-group differences in mortality and rate of unfavorable functional outcome (mRS 4–6) at 6-months that we consider “concerning” or “alarming”.

We considered a difference to be “concerning” if the 85% confidence interval (CI) of the absolute between-group difference in mortality or rates of unfavorable functional outcome (mRS 4–6) did not encompass the value of 0.0 and “alarming” if the 95% CI of the absolute between-group difference in mortality or mRS 4–6 rates did not encompass the value of 0.0.

Prior to establishing the thresholds for the 85% CI (“concerning”) and 95% CI (“alarming”) thresholds, we conducted simulations to ensure that these thresholds would yield clinically relevant differences in mortality and unfavorable functional outcome (mRS 4–6) (Figure 4). For the mortality simulations, we assumed a mortality rate of 5% in the standard care group. This selection was based on two recent similar-sized RCTs, in similar settings (Sweden [11], UK [12]), where the 6-month mortality rate was 5% in the groups treated with burr-hole craniostomy and subdural drainage. As for the mRS 4–6 simulations, we assumed an mRS 4–6 rate of 10% based on the results of the DEX-CSDH [12] and DESCA trials [13].

[figure not shown]

Figure 4. Simulation of the 95% (left panel) and 85% (right panel) confidence intervals for between-group differences in 6-month mortality rates (upper panel) and rates of mRS 4–6 (lower panel). The difference in mortality and/or rates of mRS 4–6 is significant if the 85% CI or 95% CI does not encompass the value of 0.0.

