Acknowledging that the FINISH trial was not powered for assessing differences in mortality or rate of unfavorable functional outcome (mRS 4–6), we used a 3-level hierarchy (**low** / **moderate** / **high**) for expressing our confidence in the possible between-group differences according to the GRADE approach [14–16]. We assumed a 6-month mortality rate of 5% [12,17] and an mRS 4–6 rate of 10% [12]. In terms of **mortality**, the confidence in the estimate was considered **low** if the overall 6-month mortality rate was **<5%**, **moderate** if the overall 6-month mortality rate was **5–10%**, and **high** if the overall 6-month mortality rate was **>10%**. Regarding 6-month unfavorable functional outcome (**mRS 4–6**), the confidence in the estimate was considered **low** if the rate of mRS 4–6 was **<10%**, **moderate** if the rate of mRS 4–6 was **10–15%**, and **high** if the rate of mRS 4–6 was **>15%**.

Our scheme for interpreting the possible safety concerns is outlined in Tables 3 and 4.

Table 3. A priori set thresholds for **concerning** and **alarming** between-group differences in 6-month mortality with associated confidence estimates and pre-determined commitments for interpretation.

Overall mortality in whole population	Confidence in estimate	Threshold for relevant between-group difference in mortality	Resulting action if threshold fulfilled	Authors' interpretation commitment
<5%	Low	Concerning: The 85% confidence interval of the between-group difference in absolute mortality-% does not include 0.0	None	We refrain from making any comments due to the low event rate (low confidence in effect estimate).
		Alarming: The 95% confidence interval of the between-group difference in absolute mortality-% does not include 0.0	Notion on safety concern added to the discussion (not added to the conclusion).	Group A/B was associated with an alarmingly higher mortality rate. Given the event rate, the confidence in this finding was low .
5–10%	Moderate	Concerning: The 85% confidence interval of the between-group difference in absolute mortality-% does not include 0.0	Notion on safety concern added to the discussion (not added to the conclusion).	Group A/B was associated with a concerningly higher mortality rate. Given the event rate, the confidence in this finding was moderate .

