		Alarming: The 95% confidence interval of the between-group difference in absolute mortality-% does not include 0.0	Notion on safety concern added to the conclusion.	Group A/B was associated with an alarmingly higher mortality rate. Given the event rate, the confidence in this finding was moderate .
>10%	High	Concerning: The 85% confidence interval of the between-group difference in absolute mortality-% does not include 0.0	Notion on safety concern added to the conclusion.	Group A/B was associated with a concerningly higher mortality rate. Given the event rate, the confidence in this finding was high .
		Alarming: The 95% confidence interval of the between-group difference in absolute mortality-% does not include 0.0	Notion on safety concern added to the conclusion.	Group A/B was associated with an alarmingly higher mortality rate. Given the event rate, the confidence in this finding was high .

Table 4: A priori set thresholds for concerning and alarming between-group differences in 6-month mRS4–6 with associated confidence estimates and pre-determined commitments for interpretation

Overall mRS 4–6 in whole population	Confidence in estimate	Threshold for relevant between-group difference in mRS 4–6	Resulting action if threshold fulfilled	Authors' interpretation commitment
<10%	Low	Concerning: The 85% confidence interval of the between-group difference in absolute mRS 4–6 rate does not include 0.0	None	We refrain from making any comments due to the low event rate (low confidence in effect estimate).
		Alarming: The 95% confidence interval of the between-group difference in absolute mRS 4–6 rate does not include 0.0	Notion on safety concern added to the discussion (not added to the conclusion).	Group A/B was associated with an alarmingly higher rate of unfavorable functional outcome. Given the event rate, the confidence in this finding was low .
10-15%	Moderate	Concerning: The 85% confidence interval of the between-group difference in absolute mRS 4–6 rate does not include 0.0	Notion on safety concern added to the discussion (not added to the conclusion).	Group A/B was associated with a concerningly higher rate of unfavorable functional outcome. Given the event rate, the confidence in this finding was moderate .

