		Alarming: The 95% confidence interval of the between-group difference in absolute mRS 4–6 rate does not include 0.0	Notion on safety concern added to the conclusion.	Group A/B was associated with an alarmingly higher rate of unfavorable functional outcome. Given the event rate, the confidence in this finding was moderate .
>15%	High	Concerning: The 85% confidence interval of the between-group difference in absolute mRS 4–6 rate does not include 0.0	Notion on safety concern added to the conclusion.	Group A/B was associated with a concerningly higher rate of unfavorable functional outcome. Given the event rate, the confidence in this finding was high .
		Alarming: The 95% confidence interval of the between-group difference in absolute mRS 4–6 rate does not include 0.0	Notion on safety concern added to the conclusion.	Group A/B was associated with an alarmingly higher rate of unfavorable functional outcome. Given the event rate, the confidence in this finding was high .

Table 5. Safety concerns for the intention-to-treat dataset.

Variable	All patients (n=??)	Group A (n=??)	Group B (n=??)	Difference (95% CI)	Difference (85% CI)	P-value
6 mo mortality	??/n (??%)	??/n (??%)	??/n (??%)	x (x to x)	x (x to x)	??
6 mo mRS 4–6	??/n (??%)	??/n (??%)	??/n (??%)	x (x to x)	x (x to x)	??

Abbreviations: mRS=modified Ranking Scale, CI=confidence interval

Table 6. Safety concerns for the per-protocol dataset.

Variable	All patients (n=??)	Group A (n=??)	Group B (n=??)	Difference (95% CI)	Difference (85% CI)	P-value
6 mo mortality	??/n (??%)	??/n (??%)	??/n (??%)	x (x to x)	x (x to x)	??
6 mo mRS 4–6	??/n (??%)	??/n (??%)	??/n (??%)	x (x to x)	x (x to x)	??

Abbreviations: mRS=modified Ranking Scale, CI=confidence interval

Imbalance in the incidence of safety concerns (mortality and/or mRS 4–6)?

NO / YES [INCORRECT OPTION TO BE REMOVED]

If NO, the following sentence will be added to the conclusion: “There were no relevant differences in mortality or functional outcome between the groups.”

If YES, interpretation according to **Table 3** (mortality) and **Table 4** (unfavorable functional outcome)

Step 4: Unblinding of treatment groups

Having now considered both the rate of reoperations and safety concerns, we have now reached a consensus on our blinded assessment of efficacy.

Our statistician will now unblind the treatment group assignment (break the randomization code):

- Group A = Irrigation / No irrigation [**INCORRECT OPTION TO BE REMOVED**]

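### SAP 3.2 makes absence of a mortality or mRS 4–6 difference a condition of the non-inferiority claim, but Step 5 keeps the claim when one is flagged; the mRS 4–6 intervals also leave out preoperative mRS

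*SAP*

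**What the plan says.** Section 3.2 sets two conditions for claiming non-inferiority. The first is the reoperation result in both the ITT and PP analyses. The second is that "there are no relevant between-group differences in mortality (alive or dead at 6 months) or unfavorable functional outcome", judged by the approach in the blinded data interpretation (BDI) plan. For these two outcomes, "The between-group comparison of 6-month mortality and mRS 4–6 differences will be compared using 85% and 95% CIs".

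BDI Step 3 fixes the scale and the rule. A flag is raised when the interval for the "absolute between-group difference in mortality or rates of unfavorable functional outcome (mRS 4–6) did not encompass the value of 0.0": at 85% it is called concerning, at 95% alarming. Tables 3 and 4 list both levels as thresholds for a relevant difference and attach an action to each. In the moderate band, an 85% flag alone gives "Notion on safety concern added to the discussion (not added to the conclusion"), and a 95% flag gives "Notion on safety concern added to the conclusion". In the lowest band an 85% flag leads to no action.

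The results go into "Table 5. Safety concerns for the intention-to-treat dataset" and the matching PP table (Table 6). Each has counts per arm, one difference, and its 95% and 85% intervals. The sentence "The center stratification of the randomization will be accounted for in the calculation of the CI" stands in the paragraph on the primary endpoint. Baseline function, "preoperative mRS (0–3, 4–5"), appears in 3.2 only as a potential effect modifier.

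Step 5 gives the final wording. In its non-inferior row, the sentence that no irrigation was noninferior is the same whether or not a safety difference was found. A difference only adds the Table 3 or 4 statement, if that statement qualifies for the conclusion.

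**The concern.** The two rules for the claim give different answers for the same data. Under 3.2 a relevant difference removes the claim. Under Step 5 the claim stays and may gain a sentence. Step 6 copies the Step 5 text as the final interpretation, so the conflict reaches the trial's conclusion.

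The second point is efficiency. The trial was not powered for mortality or mRS 4–6, yet the plan gives their intervals a role in the claim and in where the safety statement appears. Preoperative mRS is the baseline value of the scale being compared, and its cut is already defined. Leaving it out of the mRS 4–6 interval gives up some ability to detect a true difference at almost no saving.

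**Working it through.** **1. The claim rule, case by case.** Suppose the reoperation result is non-inferior in both ITT and PP.

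| Safety result | Section 3.2, condition 2 | Step 5 |
|---|---|---|
| No flag | claim allowed | noninferior, plus a no-difference sentence |
| 85% flag only, lowest band | a relevant difference by the column title of Tables 3 and 4, so no claim | noninferior, nothing added |
| 85% flag only, moderate band | no claim | noninferior; note in the discussion only |
| 95% flag, moderate band | no claim | noninferior, plus a sentence in the conclusion |

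The rules agree only in the first row. With no true difference, one outcome is flagged in about 15% of trials at 85% and 5% at 95%. For the two outcomes in one dataset, the chance of at least one flag lies between 15% and 15 + 15 = 30% at 85%, and between 5% and 5 + 5 = 10% at 95%. The exact value depends on their overlap, since deaths are part of mRS 4–6. That is how often the two rules would part company by chance alone, depending on which flag is meant to block.

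**2. Does the unnamed formula matter?** Take 289 per arm (recalculated sample size) and 14 deaths in one arm (14/289 = 4.8%, near the plan's 5%). Wald interval: d ± z·√[p₁(1−p₁)/n + p₂(1−p₂)/n]. With 26 deaths in the other arm, d = 12/289 = 4.15 points, SE = 2.10 points, and overall mortality is 40/578 = 6.9% (moderate band).

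| Deaths v 14 | Wald 95% | Newcombe 95% |
|---|---|---|
| 25 | −0.27 to 7.88 | −0.34 to 8.08 |
| 26 | 0.03 to 8.28 | −0.03 to 8.47 |
| 27 | 0.33 to 8.67 | 0.28 to 8.86 |

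The window is one death wide. At 26 deaths the 85% interval excludes zero either way (Wald 1.12 to 7.18; Newcombe 1.11 to 7.27), so only the placement of a sentence changes. A continuity correction moves the 95% threshold to 28 deaths and the 85% threshold from 23 to 24. Stratifying by centre, with assumed centre sizes, changes the flag in about 1% of trials or fewer.

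**3. Stratifying mRS 4–6 by preoperative mRS.** The plan gives the 10% rate and, through the sample size, 289 per arm. Assumed, because the plan gives neither: preoperative mRS 4–5 in 20% or 40% of patients, and an odds ratio of 1.5, 3 or 6 between preoperative and 6-month mRS 4–6.

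With no treatment effect, the crude variance is 2p(1−p)/n, with p(1−p) = 0.10 × 0.90 = 0.0900. The stratified variance replaces this by Σ fₖpₖ(1−pₖ).
- Odds ratio 3, 20% in mRS 4–5: stratum risks 7.57% and 19.72% average to 10%. 0.8 × 0.0700 + 0.2 × 0.1583 = 0.0876; SE ratio √(0.0876/0.0900) = 0.987.
- Odds ratio 6, 20%: risks 5.78% and 26.89%. 0.8 × 0.0545 + 0.2 × 0.1966 = 0.0829; ratio 0.960.
- Odds ratio 6, 40%: risks 3.82% and 19.26%. 0.6 × 0.0367 + 0.4 × 0.1555 = 0.0843; ratio 0.968.
- Odds ratio 1.5: ratio 0.998 to 0.999.

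Simulation (200,000 trials per setting, Mantel–Haenszel risk difference with Sato variance, two strata) confirms these ratios. The chance of a flag with a true log odds ratio of 0.45, that is 10% v about 14.3–14.8%, is:

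| Odds ratio | 85%: crude → stratified | 95%: crude → stratified |
|---|---|---|
| 1.5 | 62.8 → 62.8–63.0 | 42.1–42.3 → 42.3–42.5 |
| 3 | 60.8–60.9 → 61.8 | 40.0–40.1 → 41.2 |
| 6 | 56.7–57.6 → 59.6–60.1 | 35.9–36.9 → 38.8–39.5 |

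With no true difference, flag rates are 14.9–15.1% and 4.9–5.1% crude, and 15.0–15.2% and 5.0–5.1% stratified: no inflation either way.

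**The case against.** On the claim rule, two defences are available. Condition 2 refers to the BDI approach, so Step 5 could be its working form. Step 5 also speaks only of preventing reoperations, which is narrower than treatment non-inferiority. But the plan draws no such distinction. Step 5 has no row in which the wording is withheld because of a flag, and section 3.2 says the claim is made only if both conditions hold. The contradiction stands.

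On the intervals, most of the opposing case is right. Counts per arm followed by one difference are naturally read as crude, and a crude interval is valid. Adjustment is an improvement and not a correction, and its size rests on odds ratios and prevalences that the plan does not give. What remains is that the variable is already collected and categorised, and that stratifying by it costs essentially nothing even when it is a weak predictor.

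A reader might infer that without a named method the safety intervals are unsound, or that the method could be chosen to suit one treatment. The document does not support this. Scale, levels, rule and datasets are fixed, and the statistician works on arms coded A and B. Figure 4, which shows simulated intervals, is not available, so it cannot be checked for a method.

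**Conclusion.** Section 3.2 and Step 5 contradict each other on whether a flagged difference in mortality or mRS 4–6 prevents the non-inferiority claim. This part is wrong as written and rests on no assumption. It does not follow that an unjustified claim will be made: the plan simply does not say which rule governs.

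Stratifying the mRS 4–6 intervals by preoperative mRS is a small, nearly free gain. At an assumed odds ratio of 3, the standard error falls by about 1% and the chance of flagging a true difference rises by about 1 point. At 6 the figures are about 3–4% and 2–3 points; at 1.5 the gain is about nil.

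It would be tempting to say that the unnamed formula decides condition 2. The figures do not bear that out: it matters only within an event or two of a threshold, and in the 14 v 26 example the 85% flag is unchanged. Overall this is a minor point.

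**What to change.** Before the treatment code is broken:

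1. Reconcile condition 2 in section 3.2 with Step 5. State whether a concerning flag, an alarming flag, both or neither blocks the non-inferiority claim, or whether a flag only adds the Table 3 or 4 statement. Then give both places the same rule. If a flag blocks the claim, Step 5 needs a row for that case; if it does not, condition 2 should say so.
2. In section 3.2 and under Tables 5 and 6, state that the 85% and 95% intervals for mRS 4–6 are for the Mantel–Haenszel risk difference with Sato variance, stratified by preoperative mRS (0–3, 4–5). Read the flags from these intervals and show the crude difference alongside. Centre strata are optional.

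The cost is one sentence in 3.2, two footnotes, an edit to Step 5 and a few lines of code. There are two small downsides: the adjusted difference will not exactly equal the difference between the tabulated percentages, and patients with no preoperative mRS need a stated stratum.

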3.3 Summary of **changes** to the original statistical analysis plan

Original	Final
We will claim non-inferiority of single burr-hole evacuation without irrigation and subdural drainage only if this outcome is supported both by the ITT and the PP analysis.	
We will claim treatment non-inferiority only if:
 
1) Our primary efficacy analysis, based on the primary outcome, shows non-inferiority and the finding is supported both by the ITT and the PP analyses,
 
and

	
2) there are no relevant between-group differences in mortality (alive or dead at 6 months) or unfavorable functional outcome (mRS 0–3 vs. 4–6 at 6 months) between the groups (according to an approach outlined in the BDI).

Exploratory analyses of secondary and other binary endpoints will be performed using the χ^2 test or logistic regression analysis. Continuous outcomes will be analyzed using Student's t-test or analysis of covariance.	Exploratory analyses of secondary and other binary endpoints will be performed using the χ^2 test or logistic regression analysis. Continuous outcomes will be analyzed using regression Student's t-test, analysis of covariance or regression models .
Potential effect modifiers (patient age, unilateral vs bilateral CSDH, use of antithrombotic medication, preoperative mRS and preoperative clinical status, hematoma density, hematoma size and presence of membranes on preoperative imaging) will be analyzed by including interaction terms in statistical models.	
Potential effect modifiers will be analyzed by including interaction terms in statistical models for the following subgroups:
 
 - patient age (<70 years, ≥ 70 years) - GCS score at baseline (9–12, 13–14, 15) - history of head trauma (<4 weeks, ≥ 4 weeks, head trauma with unknown timing, no head trauma) - unilateral versus bilateral CSDH - use of anticoagulation and/or antiplatelet medication versus none - preoperative mRS (0–3, 4–5) - hematoma density (isodense, mixed-density, hypodense) - hematoma size (width in mm) - presence of membranes on preoperative imaging (yes, no)
	
The between-group comparison of 6-month mortality and mRS 4–6 differences will be compared using 85% and 95% CIs (as outlined in the BDI).

The final SAP plan was approved by:

 Jun 27, 2023
 [name] (Jun 27, 2023 00:01 GMT+3) [name] (SCM, methods PI)

 Jun 28, 2023
 [name] (Jun 28, 2023 10:49 GMT+2) [name] (trial statistician)

 Jun 27, 2023
 [name] (Jun 27, 2023 07:13 GMT+3) [name] (SCM, trial PI)

 Jun 27, 2023
 [name] (Jun 27, 2023 23:06 GMT+3) [name] (SCM, BDI committee co-chair)

[figure not shown]
 Jun 27, 2023
 [name] (Jun 27, 2023 10:56 GMT+3) [name] (SCM, BDI committee chair)

*SCM = Steering Committee Member of the FINISH trial

4. Blinded data interpretation (BDI)

The data will be interpreted according to a blinded data interpretation scheme we have published and described in detail previously [9]. In brief, the FINISH statistician (TC) will carry out the statistical analyses, blinded to the group assignment, and presents the data as Group A and Group B. The FINISH Blinded Data Interpretation committee will then contemplate the blinded results until a consensus on the interpretation is reached. Once the Blinded Data Interpretation committee reaches a consensus, the data will be unblinded and no changes are made to the interpretation of the results.

The sequence of events to take place in the upcoming ‘blinded data interpretation meeting’ is outlined in the flow chart below:

The final BDI plan was approved by:

Jun 27, 2023
[name] (Jun 27, 2023 07:13 GMT+3)
[name] (trial PI)

Jun 27, 2023
[name] (Jun 27, 2023 00:01 GMT+3)
[name] (local PI, SCM)

Jun 27, 2023
[name] (Jun 27, 2023 08:43 GMT+3)
[name] (local PI, SCM)

Jun 28, 2023
[name] (Jun 28, 2023 15:02 GMT+3)
[name] (local PI, SCM)

Jun 27, 2023
[name] (Jun 27, 2023 08:33 GMT+3)
[name] (local PI, SCM)

Jun 27, 2023
[name] (Jun 27, 2023 08:21 GMT+3)
[name] (local PI, SCM)

Jun 27, 2023
[name] (Jun 27, 2023 14:13 GMT+3)
[name] (SCM)

Jun 27, 2023
[name] (Jun 27, 2023 07:55 GMT+3)
[name] (SCM)

Jun 28, 2023
[name] (Jun 28, 2023 10:49 GMT+2)
[name] (trial statistician)

Jun 27, 2023
[name] (Jun 27, 2023 18:40 GMT+2)
[name] (BDI committee member)

Jun 27, 2023
[name] (Jun 27, 2023 09:55 GMT+3)
[name] (SCM, BDI committee member)

Jun 27, 2023
[name] (Jun 27, 2023 23:06 GMT+3)
[name] (SCM, BDI committee co-chair)

Jun 27, 2023
[name] (Jun 27, 2023 10:56 GMT+3)
[name] (SCM, BDI committee chair)

*SCM = Steering Committee Member of the FINISH trial

Minutes of the BDI**[BLINDED VALUES TO BE ADDED BY TRIAL STATISTICIAN PRIOR TO THE BDI MEETING]****Step 1: Analysis of efficacy (primary, non-inferiority analysis)**

Is no intraoperative irrigation non-inferior to irrigation in preventing symptomatic CSDH recurrence that requires reoperation after burr-hole craniostomy and subdural drainage in patients with CSDH? Based on the data in Table 2 and Figures 2 and 3, we will make an initial (blinded) interpretation on efficacy. Table 1 below describes the baseline characteristics of the study population.

Table 1. Baseline characteristics of the participants randomly assigned to irrigation or no irrigation.

Characteristic	Group A (n=??)	Group B (n=??)
Age – yr		
Female sex – no./total no. (%)		
Medical comorbidities – no./total no. (%)		
Diabetes mellitus		
Cardiac arrhythmia		
Previous cerebrovascular event		
Hypertension		
Ischemic heart disease or peripheral artery disease		
Cardiac valve prosthesis		
Pulmonary embolism or deep vein thrombosis*		
Dementia		
History of head trauma – no./total no. (%)		
Yes		
No		
Unknown		
Preoperative use of antithrombotic medication – no./total no. (%)		
No		
Antiplatelet		
Anticoagulant		
Symptoms at admission – no./total no. (%)		
Gait disturbance or falls		
Hemiparesis		
Speech disturbance		
Cognitive impairment		
Headache		
Seizure		
Other		
GCS at admission – no./total no. (%)		
15		
13–14		
9–12		
mRS at admission – no./total no. (%)		
1–3		
4–5		
Midline shift – mm		
Hematoma laterality† – no./total no. (%)		
Unilateral		
Bilateral		
Hematoma width, mm – mean (sd)		
Unilateral		
Bilateral‡		
Hematoma density§ – no./total no. (%)		
Isodense		
Hypodense		
Mixed density		
Hematoma membranes§ – no./total no. (%)		
Yes		
No		

* within 12-months before admission

† patient may have a hematoma not operated on

‡ sum of left and right hematoma widths

§ presented as individual hematomas

Abbreviations: GCS=Glasgow Coma Scale, mRS=modified Rankin Scale, SD=Standard Deviation, yr=years

[figure not shown]
Figure 1. Trial flow chart.

Table 2. Primary outcome at the primary outcome assessment time point (6 months).

Variable	Group A	Group B	Difference (97.5% CI)	P-value
Intention-to-treat				
Secondary surgery for recurrent CSDH	n=?? ??/n (x%)	n=?? ??/n (??%)	x (x to x)	??
Per-protocol-treated				
Secondary surgery for recurrent CSDH	n=?? ??/n (x%)	n=?? ??/n (??%)	x (x to x)	??

Abbreviations: CSDH=chronic subdural hematoma, CI=confidence interval

Our judgment on the efficacy (non-inferiority) will be based on the location of the whole CI in relation to Δ (non-inferiority margin) [10].

[figure not shown]

As we will not have knowledge of treatment group assignment (whether Group A or Group B is our “new treatment”, here, no irrigation), and to preserve our blinding, we have deemed it necessary to take both scenarios under consideration, as follows:

[figure not shown]
- We will calculate the treatment group difference assuming first that Group A is the “new treatment” and then that Group B is the “new treatment” (Scenario 1 and Scenario 2).
- We will plot the resulting point estimate with confidence intervals (97.5% CIs) into two separate graphs.
- We will interpret both graphs (Figures 2 and 3).

Figure 2. Scenario 1 – Group A minus Group B.

[EXAMPLE GRAPH BELOW, to be replaced by the actual graph of the FINISH trial data]

**Figure 3.** Scenario 2 – Group B minus Group A.

[EXAMPLE GRAPH BELOW, to be replaced by the actual graph of the FINISH trial data]

Step 2: Initial interpretation of efficacy

Based on the location of the whole CI in relation to Δ (non-inferiority margin), our initial interpretation on the non-inferiority of no irrigation vs. irrigation, is as follows:

Scenario 1 (Figure 2) [INCORRECT OPTION TO BE REMOVED]

1. Among adults with symptomatic chronic subdural hematoma who had undergone burr-hole drainage, Group A was [superior A / non-inferior B, C, D / inferior H] to Group B in preventing reoperations.

OR

2. Among adults with symptomatic chronic subdural hematoma who had undergone burr-hole drainage, the effect of Group A compared to Group B in preventing reoperations was inconclusive [E, F, G].

Scenario 2 (Figure 3) [INCORRECT OPTION TO BE REMOVED]

3. Among adults with symptomatic chronic subdural hematoma who had undergone burr-hole drainage, Group B was [superior A / non-inferior B, C, D / inferior H] to Group A in preventing reoperations.

OR

4. Among adults with symptomatic chronic subdural hematoma who had undergone burr-hole drainage, the effect of Group A compared to Group B in preventing reoperations was inconclusive [E, F, G].

Step 3: Analysis of safety concerns

Given that the objective of surgery for CSDH extends beyond preventing reoperations to also encompass the improvement of neurological function and prevention of death, the entire treatment effect of intraoperative irrigation (versus no irrigation) may not be adequately captured by focusing solely on the primary outcome measure, the rate of reoperations. We deemed it crucial to also consider the potential impact of between-group differences in deaths and/or unfavorable functional outcomes, as both could have an effect on the rate of reoperations. We felt that in the name of transparency and trustworthiness, we would need to define *a priori* thresholds for between-group differences in mortality and rate of unfavorable functional outcome (mRS 4–6) at 6-months that we consider “concerning” or “alarming”.

We considered a difference to be “concerning” if the 85% confidence interval (CI) of the absolute between-group difference in mortality or rates of unfavorable functional outcome (mRS 4–6) did not encompass the value of 0.0 and “alarming” if the 95% CI of the absolute between-group difference in mortality or mRS 4–6 rates did not encompass the value of 0.0.

Prior to establishing the thresholds for the 85% CI (“concerning”) and 95% CI (“alarming”) thresholds, we conducted simulations to ensure that these thresholds would yield clinically relevant differences in mortality and unfavorable functional outcome (mRS 4–6) (Figure 4). For the mortality simulations, we assumed a mortality rate of 5% in the standard care group. This selection was based on two recent similar-sized RCTs, in similar settings (Sweden [11], UK [12]), where the 6-month mortality rate was 5% in the groups treated with burr-hole craniostomy and subdural drainage. As for the mRS 4–6 simulations, we assumed an mRS 4–6 rate of 10% based on the results of the DEX-CSDH [12] and DESCA trials [13].

[figure not shown]

Figure 4. Simulation of the 95% (left panel) and 85% (right panel) confidence intervals for between-group differences in 6-month mortality rates (upper panel) and rates of mRS 4–6 (lower panel). The difference in mortality and/or rates of mRS 4–6 is significant if the 85% CI or 95% CI does not encompass the value of 0.0.

Acknowledging that the FINISH trial was not powered for assessing differences in mortality or rate of unfavorable functional outcome (mRS 4–6), we used a 3-level hierarchy (**low** / **moderate** / **high**) for expressing our confidence in the possible between-group differences according to the GRADE approach [14–16]. We assumed a 6-month mortality rate of 5% [12,17] and an mRS 4–6 rate of 10% [12]. In terms of **mortality**, the confidence in the estimate was considered **low** if the overall 6-month mortality rate was **<5%**, **moderate** if the overall 6-month mortality rate was **5–10%**, and **high** if the overall 6-month mortality rate was **>10%**. Regarding 6-month unfavorable functional outcome (**mRS 4–6**), the confidence in the estimate was considered **low** if the rate of mRS 4–6 was **<10%**, **moderate** if the rate of mRS 4–6 was **10–15%**, and **high** if the rate of mRS 4–6 was **>15%**.

Our scheme for interpreting the possible safety concerns is outlined in Tables 3 and 4.

Table 3. A priori set thresholds for **concerning** and **alarming** between-group differences in 6-month mortality with associated confidence estimates and pre-determined commitments for interpretation.

Overall mortality in whole population	Confidence in estimate	Threshold for relevant between-group difference in mortality	Resulting action if threshold fulfilled	Authors' interpretation commitment
<5%	Low	Concerning: The 85% confidence interval of the between-group difference in absolute mortality-% does not include 0.0	None	We refrain from making any comments due to the low event rate (low confidence in effect estimate).
		Alarming: The 95% confidence interval of the between-group difference in absolute mortality-% does not include 0.0	Notion on safety concern added to the discussion (not added to the conclusion).	Group A/B was associated with an alarmingly higher mortality rate. Given the event rate, the confidence in this finding was low .
5–10%	Moderate	Concerning: The 85% confidence interval of the between-group difference in absolute mortality-% does not include 0.0	Notion on safety concern added to the discussion (not added to the conclusion).	Group A/B was associated with a concerningly higher mortality rate. Given the event rate, the confidence in this finding was moderate .
		Alarming: The 95% confidence interval of the between-group difference in absolute mortality-% does not include 0.0	Notion on safety concern added to the conclusion.	Group A/B was associated with an alarmingly higher mortality rate. Given the event rate, the confidence in this finding was moderate .
>10%	High	Concerning: The 85% confidence interval of the between-group difference in absolute mortality-% does not include 0.0	Notion on safety concern added to the conclusion.	Group A/B was associated with a concerningly higher mortality rate. Given the event rate, the confidence in this finding was high .
		Alarming: The 95% confidence interval of the between-group difference in absolute mortality-% does not include 0.0	Notion on safety concern added to the conclusion.	Group A/B was associated with an alarmingly higher mortality rate. Given the event rate, the confidence in this finding was high .

Table 4: A priori set thresholds for concerning and alarming between-group differences in 6-month mRS4–6 with associated confidence estimates and pre-determined commitments for interpretation

Overall mRS 4–6 in whole population	Confidence in estimate	Threshold for relevant between-group difference in mRS 4–6	Resulting action if threshold fulfilled	Authors' interpretation commitment
<10%	Low	Concerning: The 85% confidence interval of the between-group difference in absolute mRS 4–6 rate does not include 0.0	None	We refrain from making any comments due to the low event rate (low confidence in effect estimate).
		Alarming: The 95% confidence interval of the between-group difference in absolute mRS 4–6 rate does not include 0.0	Notion on safety concern added to the discussion (not added to the conclusion).	Group A/B was associated with an alarmingly higher rate of unfavorable functional outcome. Given the event rate, the confidence in this finding was low .
10-15%	Moderate	Concerning: The 85% confidence interval of the between-group difference in absolute mRS 4–6 rate does not include 0.0	Notion on safety concern added to the discussion (not added to the conclusion).	Group A/B was associated with a concerningly higher rate of unfavorable functional outcome. Given the event rate, the confidence in this finding was moderate .
